# AHCL arm: Medtronic MiniMed™ 670G 4.0 / 780G for 6 months OR

#### Conventional arm: Standard care for 6 months. This will be followed by an optional extension phase for another 6 months.

The study will be conducted at four tertiary paediatric diabetes centres (Perth Children's Hospital, WA, Westmead Children's Hospital, NSW, Women's and Children's Hospital, SA, and Royal Children's Hospital, VIC). A home visit may be offered for some visits which involve insertion or return of blinded sensors prior to randomisation, mid and end of the study. This provides a patient centric approach working within the parameters of local policies and procedures on home visits.

**Pre-screening**: HbA1c, and fasting C-peptide for eligibility will be required, to occur within 3 months of formal screening.

All participants on CGM are encouraged to wear their sensor in the weeks preceding Visit 1.

#### VISIT 1: 1-2 hrs . (Eligibility Confirmation, Baseline data collection).

Information sheets will be provided in advance to participants who potentially fit inclusion criteria. Participants will be checked if they meet the inclusion criteria listed in Section 5.2. All post menarche females will have a urine  $\beta$ HCG test to exclude pregnancy. The following data will be recorded:

- 1. Consent signed by participant and investigator
- 2. Auxological
  - a. Height
  - b. Weight
  - c. BMI
  - d. Blood pressure
- 3. Demographic
  - a. Date of Birth
  - b. Gender
- 4. Diabetes clinical
  - a. Date of diagnosis
  - b. C-peptide (<0.1nmol/L cut off within 3 month of screening visit)
  - c. HbA1c
  - d. βHCG for all post menarche females
  - e. History of severe hypoglycaemia coma or convulsion or episodes requiring third party assistance (events in last 12 months).
  - f. History of diabetic ketoacidosis in the last 12 months
  - g. Hospital admissions in the last 12 months (DKA, Hyperglycaemia, Hypoglycaemia, Non diabetes related)
  - h. Total daily dose of insulin (mean of previous 7 days)
  - i. Co-morbidities and medications
  - j. Smoking and alcohol intake
  - k. Sensor data in the 2 weeks prior to the study (in participants on CGM).
- 5. Psychology measures:

Psychological scales will be administered on an electronic platform.

- a. Functional health status: Quality of Life: EQ-5D-3L for 12 to ≤25yrs
- b. Diabetes specific quality of life: PedsQL Child version (<13 yrs), Adolescent version (13 to <18yrs) and young adult version (18 to ≤25 yrs)

- c. Fear of hypoglycaemia: Hypoglycaemic Fear Survey-II Worry scale: 17 to ≤25yrs. Children's Hypoglycaemia Fear survey 12 to <17 yrs.
- d. Impact and Satisfaction: Diabetes Technology Questionnaire, Baseline version (all ages)
- e. Diabetes distress: Problem Areas in Diabetes (Paediatric version 12 to <18 yrs, Standard version ≥18 yrs, Parent version)
- f. Hypoglycaemia Awareness: Hypoglycaemia Awareness Scale (Gold Score) (all ages)
- g. Generalized Anxiety Disorder-7 and Patient Health Questionnaire-9 (12 to 25 years)
- h. Physical activity: The Active Australia Survey (all ages)
- 6. Insertion of the first blinded CGM (4th generation sensor and transmitter) to collect baseline glycaemic data. This constitutes first of the two sensors, each sensor provides data for 7 days. Participants will be instructed to test minimum 4x/day using CONTOUR® NEXT LINK 2.4 glucometer. At this visit, all participants will be provided with CONTOUR® NEXT LINK 2.4 glucometer and a participant record book

#### Figure 1: Schematic representation of the study design

\*CGM data from participants on CGM

#### VISIT 2

*Visit 2A:* Insertion of 2nd blinded CGM

Participants will return 7 days after sensor insertion to download the first week of CGM data. The CONTOUR® NEXT LINK 2.4 glucometer will be uploaded. A new sensor will be inserted and a fresh transmitter attached.

VISIT 2B: The blinded CGM is removed a week after insertion.

If the first or second sensor fail and/or the total readings are <70% for 10 days, a supplemental visit will be organised for a third sensor. Participants are not to have more than 4 sensors for the study. If the maximum of 4 sensors is reached and the required valid sensor glucose readings are not obtained during the run-in period, participant will be withdrawn from the study.

#### VISIT 3 (4-6 hours)

This visit is the randomisation visit, and allocation is dependent on the stratifications detailed in Section 4.3.

The following data will be collected prior to randomisation:

- 1. Diabetes clinical
  - a. HbA1c
  - b. Total daily dose of insulin (mean of previous 7 days)
  - c. Severe hypoglycaemia in the run-in period
  - d. Diabetic ketoacidosis in the run-in period
  - e. Admissions in the run-in period
  - f. Pump upload
  - g. Sensor data in the 2 weeks prior to the study (in participants on CGM)
- 2. Diabetes education/review
  - a. Diabetes education: Diabetes educator session (2 to 4 hrs) as refresher to re-educate and optimise standard diabetes management
  - b. Carbohydrate Counting: Dietician review (1 to 2 hours)
     The duration of the session is variable according to the prior knowledge of the participant.
- 3. Retinal photographs, will be collected and retained for centralised assessment
- 4. INSPIRE questionnaire (baseline for participants randomised to AHCL)
- 5. Medtronic AHCL System Background Patient Questionnaire (optional)

6. Biomarkers

A detailed description of sample preparation for biomarkers is found in appendix

- 12mL of blood and 50mL of urine will be collected in fasting state
- a. Cell Adhesion Molecules (CAM)S
- b. Soluble vascular cell adhesion molecules sVCAM
- c. Soluble intercellular adhesion molecules sICAM
- d. s-e Selectin
- e. Oxidized Low density lipoprotein
- f. Myeloperoxidase.
- g. MicroRNA signatures for arterial, renal and retinal complications
- h. Telomerase
- i. DNA methylation/acetylation
- j. Glycomark
- k. Isoprostanes and proteomics
- I. Clotting profile

VISIT 4 (participants randomised to AHCL arm)

CSII to AHCL: Participant 780G, CGM education and AHCL training.

Visit 4A: Pump training (2 hours)

Participants will be trained on how to use the Medtronic 780G insulin pump. Participants will be provided with Roche Accu-Chek®glucometer along with the glucose strips for the study.

#### Visit 4B: CGM training (2 hours)

They will be instructed on how to link CGM on the Medtronic 780G pump and issued with Guardian Sensor 3 and the Guardian Link 3 transmitter, as well as CGM user guide. Initial low and high alarms will be set at 4.0mmol/L and 15mmol/L respectively, although these can be changed according to individual preference. Sensor naïve individuals will have familiarisation phase of 7 to 10 days to get used to wearing a sensor. Visit 4A and 4B could be combined for participants familiar with sensors.

#### Visit 4C: Commencement of AHCL (1 hour)

Once CGM data has been established for a minimum of 3 to 7 days, participant returns for face-toface instruction on AHCL use and initiation of Automode. During this visit, the sensor will be replaced to demonstrate sensor warm up and AHCL initiation, and provide an opportunity for those unfamiliar with CGM use to practice a sensor change with supervision. Upon AHCL initiation, participants will be instructed to avoid excessive exercise for 48hrs while the algorithm adapts. Participants will subsequently have weekly communication via phone call or email for support for the following 4 weeks, and upload their pump weekly. Investigators will log all time spent training and in communication with participant. Communication can be more often – as per clinical need, and logged. Visit 4D: Review of AHCL (after 4 weeks from commencement of AHCL, 1 hour) Face-to-face meeting to upload insulin pump, review CareLink reports and revise settings (CHO ratio and Insulin action time)

Participants will be issued with enough consumables for the study.

Visit 4 (participant randomised to control arm) (10 weeks after randomisation)

Visit 4A: First blinded sensor insertion

Visit 4B: Removal of blinded sensor and second blinded sensor insertion

VISIT 5 (12 weeks after randomisation; 1 hour)

The following data will be collected at the midpoint:

1 Auxological

Height, Weight, BMI, Blood pressure

- 2. Diabetes clinical
  - a. HbA1c
  - b. Total daily dose of insulin (mean of previous 7 days)
  - c. Pump upload (for both groups)
  - d. Sensor data in the 2 weeks prior to the study visit (in participants on CGM)
  - e. Clinical review
- 3. Psychological assessments
  - a. Functional health status: Quality of Life: EQ-5D-3L for 12 to ≤25yrs
  - b. Diabetes specific quality of life: PedsQL Child version (<13 yrs), Adolescent version (13 to <18 yrs) and young adult version (18 to ≤25 yrs)

  - c. Fear of hypoglycaemia: Hypoglycaemic Fear Survey-II Worry scale: 17 to ≤25yrs. Children's Hypoglycaemia Fear survey 12 to <17 yrs.
  - d. Impact and Satisfaction: Diabetes Technology Questionnaire, follow-up version (all ages: only for AHCL)
  - e. Diabetes distress: Problem Areas in Diabetes (Paediatric version 12 to <18 yrs, Standard version ≥18 yrs, Parent version)
  - f. Hypoglycaemia Awareness: Hypoglycaemia Awareness Scale (Gold Score) (all ages)
  - g. Generalized Anxiety Disorder-7 and Patient Health Questionnaire-9 (12 to 25 years)
  - h. Physical activity: The Active Australia Survey (all ages)
  - i. INSPIRE questionnaire (follow-up assessment for those on AHCL)

Participants in the intervention group will be issued with enough consumables for the study

**VISIT 6** (23 weeks after randomisation; 30 mins)

Insertion of first blinded CGM (4th generation sensor and transmitter) to collect end-of -study glycaemic data. This constitutes first of the two sensors, each sensor provides data for 7 days. Participants will be instructed to test minimum 4x/day using CONTOUR® NEXT LINK 2.4 glucometer.

VISIT 7 (24 weeks after randomisation; 30 mins)

Insertion of second blinded CGM Participants will return 7 days after sensor insertion to download the first week of CGM data. The CONTOUR® NEXT LINK 2.4 glucometer will be uploaded. A new sensor will be inserted and a fresh transmitter attached.

Medtronic AHCL System Post-Study Patient Questionnaire (Optional) Phone interview (Optional)

**VISIT 8** (26 weeks after randomisation; 2 hours)

The following data will be collected.

1. Auxological

Height, Weight, BMI, Blood pressure

- 2. Diabetes clinical
  - a. HbA1c

- b. Total daily dose of insulin (mean of previous 7 days)
- c. Carbohydrate ratios and insulin sensitivity factors
- d. Pump upload (for both groups)
- e. CGM data from second blinded CGM
- f. Sensor data in the 2 weeks prior to the study visit (in participants on CGM)
- g. Clinical review
- 3. Psychological assessments
  - 1. Functional health status: Quality of Life: EQ-5D-3L for 12 to ≤25yrs
  - 2. Diabetes specific quality of life: PedsQL Child version (<13 yrs), Adolescent version (13 to<18yrs) and young adult version (18 to ≤25 yrs)
  - 3. Fear of hypoglycaemia: Hypoglycaemic Fear Survey-II Worry scale: 17 to ≤25yrs. Children's Hypoglycaemia Fear survey 12 to <17 yrs.
  - 4. Impact and Satisfaction: Diabetes Technology Questionnaire: Follow-up version (all ages only for AHCL)
  - 5. Diabetes distress: Problem Areas in Diabetes (Paediatric version 12 to <18 yrs, Standard version ≥18yrs, Parent version)
  - 6. Hypoglycaemia Awareness: Hypoglycaemia Awareness Scale (Gold Score) (all ages)
  - 7. Generalized Anxiety Disorder-7 and Patient Health Questionnaire-9 (12 to 25 years)
  - 8. Physical activity: The Active Australia Survey (all ages)
  - 9. INSPIRE questionnaire (follow-up assessment for those on AHCL)
- 4 Retinal photographs, performed as part of the routine annual screening, will be collected and retained for centralised assessment

5 Biomarkers

- 12mL of blood and 50mL of urine will be collected in a fasting state.
  - a. Cell Adhesion Molecules (CAM)S
  - b. Soluble vascular cell adhesion molecules sVCAM
  - c. Soluble intercellular adhesion molecules sICAM
  - d. s-e Selectin
  - e. Oxidized Low density lipoprotein
  - f. Myeloperoxidase.
  - g. MicroRNA signatures for arterial, renal and retinal complications
  - h. Telomerase
  - i. DNA methylation/acetylation
  - j. Glycomark
  - k. Isoprostanes and proteomics
  - I. Clotting profile

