#### Secondary endpoints

- B) Psychosocial well-being
  - 1) Functional health status EQ-5D-3L (12 to ≤25yrs)
  - Diabetes specific quality of life: PedsQL Child version (<13 yrs), Adolescent version (13 to <18yrs) and young adult version (18 to ≤25yrs).

  - Fear of hypoglycaemia: Hypoglycaemic Fear Survey-II Worry scale: 17-≤25years. Children's Hypoglycaemia Fear survey 12 to <17yrs.

  - 4) Impact and Satisfaction: The Diabetes Technology Questionnaire, Baseline and Follow-up version (all ages)
  - 5) Diabetes distress: Problem Areas in Diabetes (Paediatric version 12 to <18yrs, Standard version ≥18yrs, Parent version)
  - 6) Hypoglycaemia Awareness: Hypoglycaemia Awareness Scale (Gold Score) (all ages)
  - 7) Generalized Anxiety Disorder-7 and Patient Health Questionnaire-9 (12 to 25 years)
  - 8) INSPIRE: Perceived benefits and burdens of automated insulin delivery (all ages Intervention only)
  - 9) Physical activity: The Active Australia Survey (all ages)
  - 10) Semi structure interview (all ages post study only)
- C) *Glycaemic outcomes:* -Percent time in range
- D) -CGM data: (time in hypoglycaemia, time in range, and time in hyperglycaemia)
  - a. % CGM Time <2.8 mmol/L
  - b. % CGM Time <3.3 mmol/L
  - c. % CGM Time <3.9 mmol/L
  - d. % CGM Time 3.9-7.8 mmol/L
  - e. % CGM Time >10.0 mmol/L
  - f. % CGM Time >13.9 mmol/L
  - g. % CGM Time >16.7 mmol/L
  - h. Standard Deviation and Coefficient of Variation of CGM values
- E) Changes in retinopathy scores and retinal microvascular structure (arteriolar or venular dilation, increased vascular fractal dimension, branching and tortuosity)
- F) Human factors:

Describe participant technology interaction, adherence patterns and approaches to improve interaction.

G) Health-economic

Report the health economic impact of the MiniMed ™ 670G / 780G Insulin Pump Hybrid Closed Loop System Vs standard therapy. The following data points will be used as part of the economic analysis:

- 1) QALYs calculated from the EQ-5D-3L
- 2) Hypoglycaemic events and HbA1c
- 3) Participant reporting on work interruption
- 4) Investigator reporting time spent on training, education and support, by the type of health professional resource used
- 5) Diabetes management consumables (glucose strips, ketone strips, batteries, sensors, site dressings, lancets, needles, insulin).

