#### Visit 9A: Pump training and questionnaires (2 hours)

Participants will be trained on how to use the Medtronic 780G insulin pump. Participants will be provided with Roche Accu-Chek®glucometer along with the glucose strips for the study.

Questionnaires: INSPIRE (baseline), Diabetes Technology Questionnaire (baseline)

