#### Primary study phase

Data collected and baseline and Visit 8 (i.e. prior to 'extension phase') will be used to assess the effectiveness of AHCL therapy as compared to standard therapy.

The primary analysis will assess differences in time in range (%) with hybrid closed-loop versus standard therapy, measured six months post-randomisation using analysis of covariance (ANCOVA) with adjustment for baseline time in range. Least square means and least square mean differences and their associated 95% confidence intervals will be presented for each treatment group and between groups.

Model residuals will be used to assess model fit. If the residuals indicate poor model fit, the outcome variable will be transformed and the model refitted and evaluated. If poor model fit cannot be addressed, nonparametric analysis will be performed. In the event that residuals are not normally distributed: the Mann–Whitney–Wilcoxon (Wilcoxon Rank-Sum) Test will be employed if raw data are symmetric; if raw data are non-symmetric, bootstrap methods will be used to test the difference between groups.

Continuous secondary outcomes (glycaemic, auxological, clinical, psychosocial) will be analysed using the ANCOVA approach described above.

Secondary analysis for outcomes collected at multiple time points will be conducted using linear mixed models including random effects and various variance-covariance structures to account for non-independence. Akaike information criterion (AIC) will be used to determine the most appropriate model.

No interim analyses are planned apart from the DSMB safety review reported above.

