#### Diabetes Technology Questionnaire Part 1: Impact and Satisfaction Follow-Up Version

Thank you for giving us your time and effort in taking part in this study. Your opinions about using diabetes technology are very valuable to us and we hope that you can now help us learn how this has affected your daily life with diabetes. Below you will see some statements about different kinds of diabetes treatments that include using different diabetes devices such as a blood glucose meter, insulin pump, continuous glucose monitor or closed loop insulin delivery system.

Please tick the box below that lists the diabetes devices you are using now as part of treatment. If you aren't sure, ask the diabetes nurse to help you.

Glucose Meter(s) and daily use of an insulin pump

Glucose Meter(s) and a Continuous Glucose Monitor (Medtronic, Dexcom or Libre) and daily use of an insulin pump

For those completing a follow-up study visit: Now we'd like to ask you some questions about the treatment approach that you selected above. We've listed below some parts of living with diabetes that might be made better or worse by your use of diabetes devices. For each of these, please circle the number that best tells how much of a problem it is now and then circle the number that best tells how it has changed for you compared to the treatment received before you entered this study.

	Is this a problem now?				 	Hov you	v has i ir treat	t char ment	nged o befor	compared e the stud	mpared to the study? Much Better 5 5 5 5	
	Very Much		Just A Little		Not At All	Much Worse	A Little Worse	ہ Same	Little Better	Much Better		
1. Worry or fear about high blood sugar	1	2	3	4	5	1	2	3	4	5		
2. Effort to keep low blood sugar from happening	1	2	3	4	5	1	2	3	4	5		
3. Worry or fear about low blood sugar during sleep	1	2	3	4	5	1	2	3	4	5		

 
Feeling different from others
 
	1	2	3	4	5	1	2	3	4	5		
5. Amount of time spent thinking about diabetes	1	2	3	4	5	1	2	3	4	5		

Not knowing how eating affects blood sugar

	1	2	3	4	5	1	2	3	4	5		

 
Amount of time and effort needed for diabetes from my family or me
 
	1	2	3	4	5	1	2	3	4	5		

	s	this a	proble	m no	w?	Hov you	v has i ur treat	t char tment	nged ( befor	compared re the stud	to ly?
	Very Much		Just A Little		Not At All	Much Worse	A Little Worse	, Same	A Little Better	Much Better	

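### The follow-up Diabetes Technology Questionnaire is scheduled only for the AHCL arm at Visits 5 and 8, so the planned between-arm analysis cannot be fitted for this one secondary endpoint

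*Protocol*

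**What the plan says.** Protocol section 4.1 lists, among the psychosocial secondary endpoints, "Impact and Satisfaction: The Diabetes Technology Questionnaire, Baseline and Follow-up version (all ages". The bracket refers to age and no arm is named. The same list does flag a one-arm instrument where one is meant: "INSPIRE: Perceived benefits and burdens of automated insulin delivery (all ages Intervention only".

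At Visit 1, before randomisation, everyone completes the baseline form: "Impact and Satisfaction: Diabetes Technology Questionnaire, Baseline version (all ages". At Visit 5 (12 weeks) the entry is "Impact and Satisfaction: Diabetes Technology Questionnaire, follow-up version (all ages: only for AHCL", and at Visit 8 (26 weeks) it is "Impact and Satisfaction: Diabetes Technology Questionnaire: Follow-up version (all ages only for AHCL".

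Section 9.1 uses data from baseline and Visit 8 to compare AHCL with standard therapy, and adds: "Continuous secondary outcomes (glycaemic, auxological, clinical, psychosocial) will be analysed using the ANCOVA approach described above". The approach referred to is an ANCOVA adjusted for the baseline value.

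In the optional extension, controls moving to AHCL have at Visit 9A "Questionnaires: INSPIRE (baseline), Diabetes Technology Questionnaire (baseline". The follow-up DTQ is then scheduled without an arm limit at Visits 10 and 11.

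**The concern.** An ANCOVA of a 6-month score on treatment arm needs 6-month scores in both arms. For the DTQ the visit schedule collects them in one. A statistical analysis plan cannot repair this, because the data would not exist.

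The comparison at stake is a relevant one. The trial summary and section 2.1 ask whether managing AHCL is less of a challenge than routine treatment, and section 2.1 promises to explore satisfaction with diabetes technology. The DTQ asks directly about device alarms, carrying several devices, and the time and effort that diabetes takes. With only the AHCL arm measured, the randomised phase offers a before-after change in unblinded users of a new device. The extension section itself expects novelty to wear off.

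**Working it through.** **DTQ collection by visit (protocol sections 4.2 and 4.8)**

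| Visit | Timing | AHCL arm | Control arm |
|---|---|---|---|
| 1 | week -2 | baseline form | baseline form |
| 5 | week 12 | follow-up form | none |
| 8 | week 26 | follow-up form | none |
| 9A | about week 28, extension | not applicable | baseline form, extension entrants only |
| 10 and 11 | 9 and 12 months, extension | follow-up form | follow-up form, after the offer of AHCL |

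The schedule table in section 4.8 has a single row for all psychology measures and does not separate instruments or arms, so it does not settle the matter.

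**Numbers**

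1. The plan's own figure (section 9.2). Inputs: difference 1.5, SD 1.7, two-sided alpha 0.05, power 80%. The normal formula gives n per group = 2 × (1.960 + 0.842)² × 1.7² / 1.5² = 20.2, so 21. The t-test version gives 21.2, so 22 as stated. Allowing for 15% dropout, 44 / 0.85 = 51.8, so 52 against the 50 planned. The protocol's figure is reproduced closely and the point does not depend on it.
2. Controls randomised: 50 / 2 = about 25.
3. Controls with a scheduled post-baseline DTQ in the randomised phase: 0 at Visit 5 and 0 at Visit 8.
4. Expected completers if both arms were measured: 50 × 0.85 = 42.5, about 21 per arm. The 22 in section 9.2 is the number required, not the number expected to complete.

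**Can the planned analyses run without these data?**

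- *ANCOVA.* With no control outcomes at Visit 8, the treatment term cannot be estimated.
- *Mixed model for repeated outcomes (section 9.1).* In the randomised phase controls contribute only Visit 1, so their change over time cannot be estimated.
- *Multiple imputation (section 9.7).* The control outcome is absent by design. Any imputed value would come from the AHCL arm or from an outside assumption, so the imputation model would fix the treatment contrast.
- *Visit 9A.* The 30 items match the current-problem half of the follow-up form, and the questionnaire comes before Auto Mode starts at Visit 9C. It is taken only by controls who choose the extension, falls after Visit 8, and lacks the half that asks about change. The protocol gives no extension uptake. From none to all completing controls, the number with such a score runs from 0 to about 21.
- *Visits 10 and 11.* Controls in the extension have been offered AHCL by then, so the contrast with standard care is gone.

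**The case against.** The strongest reply is that the pattern looks deliberate. The limit appears at both randomised-phase follow-ups and disappears once both groups have been offered AHCL. Controls take a fresh baseline at Visit 9A, and the follow-up form asks about change since before the study, while controls stay on usual care. That is a coherent before-and-after use of the instrument, and the documents do not show that the limit is a slip. It still conflicts with section 4.1, which flags INSPIRE as one-arm and does not flag the DTQ, and with section 9.1, which makes no exception.

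Section 9.1 is indeed generic. It does not name the DTQ, and it cannot cover INSPIRE either. That makes the conflict less direct, but the unrestricted endpoint listing stands.

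The form's own treatment boxes, such as "Glucose Meter(s) and daily use of an insulin pump", show that controls could complete it. They do not show whom it was meant for, since there is no closed-loop box although AHCL users are given it.

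Two stronger readings are tempting. A reader might infer that the trial yields no between-arm information on the DTQ at all. Visit 9A contradicts this, since it gives some controls the same 30 items near 6 months while not yet on AHCL. A reader might also infer that the psychosocial aim cannot be met. The documents do not support this: EQ-5D-3L, PedsQL, the hypoglycaemia fear surveys, PAID, the Gold score, GAD-7, PHQ-9 and the activity survey are scheduled at Visits 1, 5 and 8 with no arm limit.

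**Conclusion.** The point holds for one secondary endpoint. Sections 4.1 and 9.1 imply a randomised comparison of the DTQ, and the Visit 5 and Visit 8 schedules in section 4.2 do not collect the control-arm data for it. The size is 0 of about 25 controls with a scheduled post-baseline DTQ in the randomised phase, against about 25 in the AHCL arm before dropout. Visit 9A softens this for controls who enter the extension but does not supply the planned analysis. The conclusion assumes equal allocation of 50 participants and that the visit lists are followed as printed. The primary endpoint, the sample size and the remaining psychosocial comparisons are not affected.

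**What to change.** Remove the AHCL-only limit from the DTQ entries at Visits 5 and 8 and give the follow-up form to both arms. For the between-arm ANCOVA, use the 30 current-problem items, which match the baseline form, adjusted for Visit 1. Report the items on change since before the study as supportive. This restores about 21 completers per arm at 15% dropout.

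The cost is a 30-item electronic form at two existing visits for about 25 controls, at most 50 extra forms, with no new visit.

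If a one-arm DTQ is intended, mark it in section 4.1 as intervention-only and descriptive, as is done for INSPIRE, and exclude it from the between-arm ANCOVA in section 9.1. That adds no participant burden but gives up the randomised comparison on this instrument.
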